5.3. Enrollment/Selection Strategies

5.3.1. Prospective Recruitment -or- Retrospective Selection

We have extensive experience recruiting women in the menopause transition into our clinical research studies involving transdermal estradiol interventions (three prior R01 projects). That experience tells us that Facebook is our most effective strategy for this demographic in terms of number of potentially eligible candidates (number who contact us). The UNC informational listserv is also highly effective as are flyers posted in the community (e.g., coffee shops, libraries, grocery stores). We will also advertise in periodicals or magazines that target this demographic such as *Carolina Woman*. Finally, we will notify our colleagues in the UNC Center for Women's Mood Disorders and the UNC Department of Obstetrics and Gynecology about our study and ask them to refer appropriate candidates.

5.3.2. Screen Failures

Of the estimated 50 women who pass our phone screening and come to an in-person enrollment, based on prior experience we predict that 30% (n=15) will not meet eligibility for TE2 after personal and family history review during enrollment or will not meet reproductive staging criteria based on further detailed questions about their menstrual bleeding patterns. For those women in the latter category, if it appears they are too early in the menopause transition (not yet meeting the variance in cycle length of +/- 7 days) we will obtain verbal consent to follow up with them and ask them to contact us if bleeding patterns change at which time, they will be re-screened. We also estimate that up to 15% (n =5) will decide to withdraw after enrollment. The primary reason, based on our past experience, is time commitment.

5.4. Strategies for Retention

We will rely on our successful retention strategies in our prior studies in perimenopausal women that randomized women to TE2 or placebo and followed them for up to 12 months successfully. The much shorter duration of involvement in this study (16 weeks) will naturally have a positive impact on retention. Other strategies that we have used and plan to employ include:

- Enrolling only fully informed participants using an infographic that summarizes events and timeline of
 the protocol and asking participants to restate to us risks and potential side effects of TE2 and
 progesterone during the enrollment session.
- An emphasis during staff training on the importance of effective communication strategies and establishing rapport with participants.
- Maintaining frequent communication with study visit reminders and 'check-ins'.
- Convenient free parking outside of [name] where all study visits will occur.
- Appropriate, non-coercive monetary incentive for mid-life women to acknowledge their time. Each participant who completes the entire protocol will receive \$650.
- Whenever possible, involving staff from underrepresented groups to help recruit and retain participants from underrepresented groups

5.5. Matching and Stratification

Not applicable.

5.6. Randomization and Concealment

Using a within-subjects, cross-over, placebo-controlled, double-blind design, participants will be randomized (1:1) to either three weeks of transdermal E2 (0.1 mg/day) or to three weeks of transdermal placebo as their first condition (Condition 1) and will have the other treatment (active TE2 or placebo) as Condition 2. Randomization to order of conditions will not be stratified.

[name], statistical collaborator on the project and Director of the Psychiatry Biostatistics Core, will develop the randomization table and the UNC Hospitals Investigational Drug Services will manage the randomization.

5.7. Blinding

The transdermal patches will be blinded by the UNC Hospitals Investigational Drug Services who will package active and placebo preparations into blinded, identical pouches. All study staff, investigators, and research participants will remain blind to subjects' order of active vs. placebo intervention conditions until final data collection is complete.

In the event of an adverse event that could be potentially related to the pharmacologic intervention, the gynecology collaborator, [name] will be unblinded to treatment to determine if the subject needs to be withdrawn. In that event, only [name] will be informed who will, with [name], determine the course of action for the participant (e.g., follow-up with their doctor, ultrasound if suspected DVT, etc.). [name] will not

be performing any assessments with research participants so her unblinding should not create bias in data collection, analyses, or interactions with other participants. Staff will not be informed as to the reason any particular subject is withdrawn.

6. Treatment Design: Procedures

Description

Using a within-subjects, cross-over, placebo-controlled, double-blind design, participants will be randomized (1:1) to either three weeks of transdermal E2 (0.1 mg/day) or to three weeks of transdermal placebo as their first condition (Condition 1). A three-week washout period will follow, and Condition 2 will follow the washout (placebo E2 if Condition 1 was active and active TE2 if Condition 1 was placebo). At the end of a subject's participation, each will be given Prometrium® (200 mg/day for 10 days).

Acquisition Investigational Drug Services will order the commercially available Climara® transdermal patches and the commercially available Prometrium® progesterone.

Storage Investigational drug services will store the Climara® and Prometrium® at a controlled room temperature of 77° stored away from heat, moisture, and direct light. Prometrium® will be dispensed in tight, light resistant containers. Climara® and the placebo patch will be dispensed in light resistant foil pouches. Participants will be instructed to store their study medications under the same temperature and light controlled conditions. Given the short duration of the intervention, there will not be a risk that the medications will expire.

Preparation and Administration By avoiding the first-pass metabolic effects of oral estrogen, transdermal E2 (TE2) creates more stable, premenopausal follicular phase E2 levels than oral; and a physiologic profile of E2 relative to its metabolites. TE2 also has a superior safety profile than oral estrogen. A 7-day transdermal system provides more stable levels and better compliance than twice weekly patches. The adhesive layer of the matrix in Climara® patches continuously releases E2, which is transported across skin leading to sustained E2 levels. Climara®, estradiol transdermal system, is designed to release estradiol continuously upon application to intact skin. The period of use is 7 days/patch. Progesterone: To prevent E2-induced endometrial hyperplasia, 200 mg micronized progesterone/day x 10 days will be taken at study completion. A progestin every 2-3 months is sufficient for endometrial protection, a particularly in women in the early MT who still menstruate. We will give progesterone in a discontinuous fashion instead of using Climara Pro® (delivers both E2 and a progestin) because progestins antagonize E2 effects. E25,26

Once the IDS has prepared the blinded patches or the progesterone, for each participant, that participant's medications will be stored at a controlled room temperature of 77° F in a locked file cabinet in [name] laboratory away from heat and direct light until dispensed to the participant. If there is a delay in dispensing to a participant (due to illness or other need to reschedule), this will be documented in the participant's file and in our medication dispensing log, but we will continue to hold that participant's medication for up to four weeks since both TE2 and Prometrium are stable.

Accountability For each subject, a medication dispensing log will be kept in their study file. At weekly study visits, the research staff will record number of patches and pills dispensed and the research participant will sign the log indicating receipt of the next supply. Participants will return all used and unused patches at each weekly study visit. Number of returns will be recorded in the same medication dispensing log. Returns (used and unused patches) will be returned to Investigational Drug Services for destruction.

Rescue Procedures/Medications Not applicable. Adverse events resulting from transdermal E2 would warrant discontinuation of the medication as determined by the [name]. Discontinuation of estradiol does not require a tapering schedule and there would be no 'rescue' medication.

Adherence Monitoring/Evaluations Subjects will: 1) be educated on the importance of replacing patches every 7 days and we will develop an individualized behavioral strategy to enhance compliance; 2) record date of patch

application on their calendars and receive text/call reminders; **3)** bring used and unused patches to each visit; and **4)** be given extra replacement patches. Patch counts (both used and unused) will be conducted at each weekly visit as the 'real time' assessment of compliance. Retrospectively, we can evaluate compliance by comparing urinary E1G levels under each of the two treatment conditions (transdermal E2 and placebo). If compliant, mean E1G levels should be significantly higher under the active TE2 condition.

Concomitant Therapies All psychotropic and hormonal therapies are prohibited as would insulin use. Stable thyroid hormone supplementation is allowed as is stable blood pressure medication as long as the medication is effective at maintaining blood pressure below 160/100 mmHg. Medication use will be assessed by self-report during screening and again at enrollment via the Personal and Family Health History Questionnaire.

7. Schedule of Activities and Procedures

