Study Description	The primary objective of this research is to determine the neurophysiologic basis of susceptibility to estradiol (E2) fluctuations and irritability symptoms in perimenopausal women. The rationale for examining E2 variability in perimenopausal irritability stems from the evidence that: 1) the amygdala and other limbic regions are densely innervated with E2 receptors; and 2) E2 regulates limbic feedback control of the HPA stress response, dysregulation of which may increase stress vulnerability. Urinary estrone-3-glucuronide (E1G), a urinary metabolite of E2 that is highly correlated with serum E2, will be used as the indicator of serum E2.								
	Using a within-subjects, cross-over design and transdermal E2 (TE2) to stabilize E2 fluctuations (and increase levels) we will test if neural dynamics (oscillatory activity in the theta and beta frequencies assessed via EEG) associated with key constructs of irritability (attentional bias to threat and frustration to non-reward) represent a biomarker target of irritability symptom response to TE2.								
Specific Aims (objectives)	Aim 1. Define the baseline relationships between: (a) E1G variability and irritability symptom severity; (b) E1G variability and theta and beta oscillatory correlates of threat and frustration; (c) irritability symptoms and theta and beta oscillatory correlates of threat and frustration. AIM 2: Determine whether TE2, versus placebo, will: a) beneficially modify task-evoked theta and beta oscillations (i.e., reduce theta and increase beta activation) in response to threat and frustration; and b) reduce irritability symptom severity.								
Target Population	 Inclusion Criteria: Medically healthy women, 45 – 59 years of age undergoing a natural menopause transition Moderate to severe levels of irritability symptoms Normotensive blood pressure (< 160/100 mmHg) Meet Stages of Reproductive Aging Workshop criteria for early menopause transition (STRAW+10, stage -2) or late menopause transition (STRAW +10, stage -1) based on bleeding patterns Have experienced 1+ very stressful life event in previous six months Report a significant increase in irritability concurrent with onset of menstrual cycle changes Normal screening mammogram within two years of enrollment. 								
	 A history of cardiovascular disease A history of type I diabetes A recent history of migraine with aura A history of thromboembolic disorders 								

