5. A history of E2 dependent neoplasia **6.** A history of liver dysfunction 7. A personal or family history suggesting elevated risk for E2-related cancer or thrombotic events 8. Use of psychotropics or hormonal agents **9.** A history of psychosis or bipolar disorder **10.** Suicidality with intent **11.** Current mood disorders of severity to require treatment A total of N = 50 eligible individuals will be enrolled. Based on our prior Numbers of Enrollees studies of TE2, of the estimated 50 women who pass our phone screening and come to an in-person enrollment, we predict that 30% (n=15) will not meet eligibility for TE2 after personal and family history review or will not meet reproductive staging criteria based on further detailed questions about their menstrual bleeding patterns. We anticipate that up to an additional 15% (n =5) may withdraw after enrollment, yielding 30 women who we anticipate will complete all aspects of the protocol and will have complete data. Up to 135 individuals will be recruited and screened. 40% will fail the screening for TE2 eligibility, and an additional 20% will not be interested in participating. Using a within-subjects, cross-over, placebo-controlled, double-blind Interventions or design, participants will be randomized (1:1) to either three weeks of **Exposures/Conditions** transdermal E2 (0.1 mg/day) or to three weeks of transdermal placebo as their first condition (Condition 1). Weekly mood ratings and daily ill temper (irritability) ratings will be collected across the three weeks. In week 3 of each Condition, daily E1G collections will commence (days 15-21) and the EEG session with Dot-Probe and Affective Posner Paradigm tasks will be administered (day 21). A three-week washout period will follow. Condition 2 (3 weeks) will follow the washout (placebo E2 if Condition 1 was active E2 or active E2 if Condition 1 was placebo) with identical assessments and timeline as for Condition 1. To prevent TE2-induced endometrial hyperplasia, 200 mg micronized progesterone/day for 10 days will be given to all women at study completion (Progesterone follow-up phase). **Outcome Measures** For Aim 1. Over the four-week baseline period, irritability symptoms will be measured daily using the III temper subscale of the Inventory of Depression and Anxiety Symptoms (IDAS). Urinary measures of E1G will be collected every other day (14 samples total) and assayed using an enzyme immunoassay (Arbor Assays, Ann Arbor, MI), with sensitivity at < 22.5 pg/mL to calculate within subject fluctuation in E1G (indexed by the standard deviation of E1G over the four weeks). At the end of baseline week 4, Theta and Beta oscillatory frequencies will be assessed at rest and in response to the Dot Probe task which measures attention bias to angry faces (threat attention bias) and in response to the Affective Posner Paradigm that measures relational aggression (approach behavior) in response to frustration. For Aim 2. The outcomes are identical to those in Aim 1. The primary comparison will be within subject - comparing the active TE2 condition

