
Statistical Analysis Plans for Each Aim Study Duration	to the placebo TE2 condition. Irritability symptoms will be measured daily using the III temper subscale of the Inventory of Depression and Anxiety Symptoms. Theta and Beta oscillatory frequencies will be assessed at rest and in response to the Dot Probe task and the Affective Posner Paradigm administered at the last day of each condition. Urinary measures of E1G will be collected every day during the last week of each condition and measured using an enzyme immunoassay (Arbor Assays, Ann Arbor, MI), with sensitivity at < 22.5 pg/mL to generate to within subject variability in E1G (indexed by the standard deviation of E1G). Aim 1 Plans. Linear regression models will predict irritability symptoms and theta and beta frequencies in response to tasks from E1G variability (based on the standard deviation of seven daily E1G measurements) and predict irritability symptoms from theta and beta task-related frequencies. Aim 2 Plans. The two repeated post-treatment EEG measures (theta and beta task-related frequencies) will be modeled as a function of fixed factors including baseline EEG measures (continuous), Condition status (TE2 or placebo; binary), and order of Condition (binary) in a linear mixed effects model with a random intercept accounting for the within-subject variance. The two-sided Wald test will test the significance of TE2 effects. 2b) Similarly, daily irritability symptoms (3 weeks/Condition) will be modeled as a function of fixed factors including baseline irritability symptoms (continuous), Condition, and order of Condition in a linear mixed effects model with a random intercept accounting for within-subject variance.
Participation Duration	Sixteen weeks
Enrollment Duration	Two years

2. Introduction

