Define the baseline relationships between: (a) E1G variability and irritability symptom severity; (b) E1G variability and theta and beta oscillatory correlates of threat and frustration; (c) irritability symptoms and theta and beta oscillatory correlates of threat and frustration. The estimands of interest are the correlation coefficients between a) E1G variability (standard deviation (SD) of E1G over the four-week baseline phase) and irritability symptoms b) E1G variability (SD) and theta and beta oscillatory activation during threat and frustration tasks; and c) irritability symptoms and theta and beta oscillatory activation during threat and frustration tasks.

3.2. Aim 2

Determine whether TE2, versus placebo, will: a) beneficially modify task-evoked theta and beta oscillations (i.e., reduce theta and increase beta activation) in response to threat and frustration tasks; and b) reduce irritability symptom severity. The estimands of interest are a) the mean difference (and direction of difference) between the active TE2 and placebo TE2 conditions in theta and beta activation to threat and frustration tasks and b) the mean difference (and direction of difference) between the active TE2 and placebo TE2 conditions in mean irritability symptom severity.

4. Study Design

This single site, interventional study employs a within-subjects, cross-over, placebo-controlled, double-blind design.

Stage 1: A four-week baseline assessment involving: 1) at home urine collections of E1G; 2) mood ratings (general mood and irritability specific ratings); and 3) in-lab EEG session to assess theta and beta oscillations in response to behavioral tasks designed to elicit threat reactivity (Dot Probe task) and frustration to non-reward (Affective Posner Paradigm). Four weeks was chosen to allow for a sufficient number of E1G collections (n=14) to calculate a reliable standard deviation score for each participant.

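### The plan derives an E1G standard deviation in each Condition but specifies no TE2-placebo comparison of it and no model holding both variability and level, so no planned analysis would show that TE2 reduced E2 fluctuation

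*Combined protocol and SAP*

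**What the plan says.** The Synopsis (Study Description) gives TE2 two simultaneous actions: "transdermal E2 (TE2) to stabilize E2 fluctuations (and increase levels) we will test" whether task-related neural dynamics are a biomarker target of symptom response. It schedules E1G in week 3 of each Condition: "daily E1G collections will commence (days 15-21"). Under the Aim 2 outcome measures it repeats "Urinary measures of E1G will be collected every day during the last week of each condition" and says that the samples are to yield "within subject variability in E1G (indexed by the standard deviation of E1G").

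The analysis text does not take this up:

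- Section 3.2 defines the Aim 2 estimands as "the mean difference (and direction of difference) between the active TE2 and placebo TE2 conditions in theta and beta activation", and likewise for irritability. E1G is not part of them, and the section 3 table lists none for Aim 2.
- The Aim 2 mixed models (Synopsis and section 8.3) contain the baseline value, Condition, order and a random intercept. There is no E1G term.
- Table 1 in section 4.3 lists E1G as measured at visits 7 and 13, but with the role of predictor for Aim 1 only.
- Section 8.3 hypothesises that E1G variability will predict outcomes in Aim 1 and Condition effects in Aim 2. It turns to E1G level only if the analyses do not support variability. No model is given for either step in Aim 2.
- Section 6 (Adherence Monitoring) offers the one explicit contrast of E1G between Conditions, as an option: "Retrospectively, we can evaluate compliance by comparing urinary E1G levels under each of the two treatment conditions". Its criterion is a higher mean: "If compliant, mean E1G levels should be significantly higher under the active TE2 condition".

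**The concern.** The title and primary objective concern susceptibility to E2 fluctuation, and TE2 is the tool meant to reduce it. The same patch also raises the level, and section 12.2 describes participants as still menstruating, so the patch adds to the ovaries' own varying output. The stability rationale in sections 2.2 and 4.1 compares the patch with oral estrogen and with twice-weekly patches, not with placebo. Whether TE2 lowers fluctuation relative to placebo is therefore something for this trial to check.

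Without that check, a positive Aim 2 result invites a stabilisation reading with no specified analysis behind it. A null result could not separate the possibility that fluctuation does not matter from the possibility that it was not reduced.

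The fallback rule adds a second problem. Raw SD tends to track level. If it predicts an outcome, the rule as written never brings level in, and variability gets credit that may belong to level.

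**Working it through.** The documents state no figure for any E1G contrast, so there is none to reproduce. Three checks follow.

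**1. What the mean check can show.** Its criterion is mean E1G on TE2 above mean E1G on placebo. A patch that only adds to the level satisfies it with fluctuation unchanged. It is a reasonable compliance measure, but it carries no information on stability.

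**2. How the two SD indices behave when the level moves.**

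*Proportional fluctuation.* Raw SD = mean × proportional SD. Take a doubled mean as an assumption:

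- proportional fluctuation unchanged: 2 × 1 = 2.0, raw SD doubles;
- proportional fluctuation down 25%: 2 × 0.75 = 1.5, raw SD rises 50%;
- proportional fluctuation halved: 2 × 0.5 = 1.0, raw SD is unchanged.

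Here raw SD hides or reverses a real proportional reduction.

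*Added constant.* Suppose the patch adds a constant, equal to the existing mean, to unchanged ovarian fluctuation. SD(x + c) = SD(x), so the raw SD ratio is 1.00. Simulating 7 log-normal values per woman with an assumed log-SD of 0.4-0.6, the SD of ln(E1G) falls to about 0.46-0.48 of its former value. Here the log index reports roughly a halving with no fall in absolute fluctuation.

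Each index can mislead in one of two plausible situations, so neither suffices alone.

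**3. Whether the planned samples support a between-Condition comparison.**

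Inputs: k = 7 daily values per Condition (Synopsis, days 15-21) and N = 30 completers (section 9). Two-sided alpha is 0.05, assumed because the plan does not state it. τ is the between-woman SD of the true change in ln(SD), assumed 0, 0.3 or 0.5. Daily values are taken as independent and roughly normal on the log scale.

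Sampling variance of ln(SD) = trigamma((k − 1)/2)/4. For k = 7 this is 0.395/4 = 0.0987, so the SE is 0.314.

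SD of the paired difference = √(2 × 0.0987 + τ²). For 80% power, a paired t-test at N = 30 needs a standardised difference of 0.529. Detectable ratio = exp(−0.529 × SD of difference).

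| τ | SD of difference | Detectable SD ratio | Fall | Power for a 30% fall |
|---|---|---|---|---|
| 0 | 0.444 | 0.79 | 21% | 0.99 |
| 0.3 | 0.536 | 0.75 | 25% | 0.94 |
| 0.5 | 0.669 | 0.70 | 30% | 0.81 |

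The footnote to the table in section 7.1 can be read as every-other-day sampling in the Condition weeks, against daily in the Synopsis and sections 4 and 11.2. With about 4 values (SE 0.483) the detectable ratios become 0.70, 0.67 and 0.64, and power for a 30% fall drops to 0.79, 0.72 and 0.61.

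One woman's SD is imprecise: with 7 values its 95% CI runs from 0.64 to 2.20 times the estimate. The comparison works as a group contrast, not as a classification of individual women.

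**The case against.** The strongest reply is that variability is not ignored in Aim 2. The per-Condition SD sits under the Aim 2 outcome measures, and section 8.3 states the intention to relate variability, then level, to Condition effects. The Synopsis openly says that TE2 also raises levels. The section 6 sentence is only an adherence check, for which the mean is sensible. All of this stands. It shows that the analysis is intended but not specified: there is no between-Condition test of SD, no E1G term in an Aim 2 model, and no model with both quantities.

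A reader might go further and infer that a TE2 effect can never be linked to reduced fluctuation, or that the main objective goes unanswered. The documents do not support either. The samples needed are collected, and Aim 1 relates E1G variability directly to irritability and to EEG without TE2. The Aim 2 estimands are TE2-placebo differences, which hold whatever the mechanism. Nor do the documents say that the report would credit stabilisation; that is a risk of interpretation.

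A reader might also infer that replacing raw SD with the SD of ln(E1G) settles the matter. The added-constant case shows that it does not. The plan also adopts the assay and methods of a prior study (section 4.3), which is a reason to keep raw SD for comparability.

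Finally, seven consecutive days in women who still cycle are likely to be autocorrelated and to depend on cycle phase. That is fair: the detectable falls above are best cases.

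**Conclusion.** The gap is real and limited to mechanism. The plan derives the E1G SD in each Condition and hypothesises that variability predicts Condition effects, but no specified analysis would show that TE2 reduced fluctuation or would separate fluctuation from level. The Aim 2 effect estimates are unaffected.

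A between-Condition comparison is feasible on the planned samples: about a 21-30% fall in ln-scale SD is detectable at 80% power. This rests on 7 independent daily values per Condition, N = 30, two-sided alpha 0.05 and assumed heterogeneity of 0-0.5. Autocorrelation, or fewer samples, would worsen it. The documents give no E1G distribution, so the doubling of the mean and the log-SD of 0.4-0.6 are illustrations of direction, not forecasts.

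Even a clear fall in SD would not prove that stabilisation caused a TE2 effect, because the same patch moves the level and any adjusted analysis within Condition is observational. Reduced variability is necessary for that claim, not sufficient. The change is worth making because it is cheap and bears on the trial's own mechanistic question.

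**What to change.** 1. In section 8.3 and the section 3 table, add a within-woman TE2-placebo comparison of E1G variability over days 15-21. Report both raw SD and SD of ln(E1G) (or the CV) as ratios with 95% CIs, beside the comparison of mean E1G. Correct the E1G row of Table 1 to include Aim 2, and reconcile the sampling frequency in the section 7.1 footnote with the daily schedule elsewhere.
2. Replace the rule that examines level only if variability fails. In Aim 1, report the variability models with and without mean E1G. In Aim 2, do the same as a labelled exploratory analysis.
3. State in advance that lower variability on TE2 is necessary but not sufficient to credit stabilisation. Where it is not shown, describe Aim 2 results as effects of TE2 (level and/or stability).
4. Fix this text before unblinding, since section 8.1 otherwise allows exploratory analyses designed after the outcomes are known.

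Cost: SAP wording and a few analyses on samples already planned. The downsides are wider intervals where SD and mean are collinear, and a mechanistic claim that may have to be weakened.
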